## 20.0 Provisions to Protect the Privacy Interests of Subjects

### 20.1 *Describe the steps that you will take to protect subjects' privacy interests.*

*"Privacy interest" refers to a person's desire to place limits on with whom they interact or to whom they provide personal information (e.g., collecting the minimal amount of private information required to complete the study, protecting the data once it is obtained):*

The minimal amount of private information will be collected and once the necessary data is collected all data will be unidentifiable through the use of codes and remain confidential in a locked cabinet.

### 20.2 *Describe steps that you will take to make subjects feel at ease with the research situation in terms of the questions being asked and the procedures being performed. "At ease" does not refer to physical discomfort, but the sense of intrusiveness a subject might experience in response to questions, examinations, and procedures (e.g., use of a same gender investigator to place sensors on the torso, a private changing area if clothing must be changed, sensitivity when discussing pregnancy testing with subjects, making it clear on surveys that participants can discontinue at any time, not asking questions about private or sensitive issues unless necessary for the research):*

For procedures requiring the placement of sensors on a sensitive area of the body, such as tonometry measurements (arterial stiffness) on the inner thigh, this will be performed by a same gender investigator.

There is a private changing area in our Human Integrative Physiology Laboratory for when individuals need to change into hospital gowns for the arterial stiffness and FMD measurements.

There is a private bathroom for subjects to use and for when they are required to provide a urine sample for urinalysis.

Sensitivity will be ensured when discussing pregnancy testing with subjects.

During the consenting process and throughout the investigation, subjects will be made fully aware of their rights to withdraw from a procedure or the study.

*20.3 Describe how you plan to access existing sources of information about the subjects (e.g., medical records, grades) and how you will protect participant privacy through the data security plan:*

No existing sources of information will be accessed.

*20.4 Describe any required reporting that might occur as a result of your research questions, study populations, and data collection methods. Examples for Virginia and Virginia Tech include:*

- *Any suspicions (e.g., circumstantial, disclosed) of child abuse (physical, emotional, sexual) and neglect*
- *Sexual discrimination and/or sexual violence that involves a student*
- *Disclosure or signs of intention to harm oneself (i.e., suicidal ideation and/or plan)*
- *Disclosure or signs of desire to harm others (i.e., homicidal ideation and/or plan)*
- *Suspected abuse, neglect or exploitation of vulnerable adults (e.g., individuals with a disability, elderly persons)*

We do not anticipate any required reporting from the conduct of our study. However, we will report any of the above if there is circumstantial or disclosed information to the above points.

## **21.0 Provisions to Monitor the Data to Ensure the Safety of Subjects**

*Safety monitoring is required when research involves greater than minimal risk and is sometimes appropriate for other studies.*

*21.1 Describe:*

- *The plan to periodically evaluate the data collected regarding both harms and benefits to determine whether subjects remain safe (e.g., periodic reporting to the IRB, establishing a data monitoring committee, reporting data monitoring committee findings to the IRB and the sponsor).*
- *What data you will review, including safety data, unexpected events, and data that show the ability to produce the intended results.*
- *How the safety information will be collected (e.g., with case report forms, at study visits, by telephone calls with subjects).*
- *The frequency of data collection, including when safety data collection starts.*

- *Who will review the safety data and with what frequency.*
- *The statistical tests for analyzing the safety data to determine whether harm is occurring.*
- *Any conditions that will trigger an immediate suspension of the research (e.g., a serious adverse event).*

The data safety monitoring plan (DSMP) for this study focuses on close monitoring by the principal investigator (PI) in conjunction with a safety officer ([name]), along with prompt reporting of excessive adverse events and any serious adverse events (AEs) to the NIH and to the Institutional Review Board. All serious AEs will be reported by the PI within 48 hours of occurrence to the IRB.

Safety reports will be sent to the PI and to the safety officer. The Project Coordinator ([name].) will be responsible for assembling the data and producing these reports as well as assuring that all parties obtain copies of these reports. Reports will be submitted annually to the VT IRB for review.

The frequency of data review for this study differs according to the type of data, the availability of data collected, and the perceived level of risk. Subjects will be queried at the laboratory visits when supplements are provided as to any side effects or changes in health status that they experience. Any reported side effects will be discussed immediately with the PI and if necessary (i.e., serious adverse event), with [name]. Out-of-range laboratory data (i.e., BP, bloodwork) will be discussed immediately with the PI and [name] to determine if medical intervention or other actions are warranted. Subjects will be referred to their primary care physician if there are incidental findings.

Data type	Frequency of reviewing reports
Subject accrual (adherence to the protocol regarding demographics, inclusion/exclusion)	Semi-annually
Adverse event rates	Semi-annually
Compliance to treatment	Semi-annually
Out of range laboratory data	Semi-annually
Stopping rules report regarding statistical power implications of drop outs and missing data	Semi-annually
Side effects of test meals, study procedures	Daily, when meals are picked up

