## 1.0 Study Summary

Study Title	Short Term Choline Supplementation and Cardiovascular Health in Adults
Study Design	2 x 4 crossover design with repeated measures and we will conduct descriptive univariate analyses on all study variables.
Primary Objective	To establish proof-of-concept for a greater reduction in glucose homeostasis following increases in gut microbiota-generated TMAO on glucose homeostasis in older compared with young adults in order to conduct a larger, more comprehensive and mechanistic trial in the future.
Secondary Objective(s)	- Obtain preliminary data for effect size generation.
Study Population	We are recruiting men and women who are between the ages of 18-79 years of age. We will recruit individuals of all races and ethnic backgrounds.
Sample Size	60 subjects
Research Intervention(s)/ Investigational Agent(s)	-Interventions (Choline and Placebo supplementation in capsule form)
Study Duration for Individual Participants	
How long will a participant spend in your study? If multiple sessions, list time required for each session plus total.
 
Visit: 1 = 1 hour
 
Visit: 2, 8, 11, 17 = 3 hours each
 
Visit: 3, 9, 12, 18 = 2 hours each
 
Visit: 4, 10, 13, 19 = 3 hours each
 
Visit: 5, 6, 7, 14, 15, 16 = 30 minutes each
 
Total Time: 36 hours

Acronyms and Definitions	
TMA = Trimethylamine
 
TMAO = Trimethylamine-N-oxide
 
T2D = Type 2 Diabetes
 
GI = Gastrointestinal
 
FMD = Flow mediated dilation
 
CGM = Continuous glucose monitor

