## **8.0 Procedures Involved**

*8.1 Describe and explain the study design:*

Using a randomized cross-over design, participants will be given and asked to consume either choline or a placebo (maltodextrin) supplement for four weeks and will consume 1000 mg (500 BID) of choline or placebo per day. Testing will take place over twelve visits. Participants will complete a screening visit and two periods of three-day testing sessions before and after the four-week period of choline and placebo supplement. In between experimental sessions, there will be a two-week “washout”.

*8.2 Provide a description of:*

- *All research procedures being performed*
- *If the study has more than one procedure, session, and/or subject population, describe each procedure, session, and/or study population separately. For complex studies, you are encouraged to include a figure or chart.*

Session 1: Baseline (screening) session (Approximately 2 hours) Garvin Building, Suite 1575

Overnight Fast: Subjects will be asked to avoid eating or drinking anything except water and to avoid consuming any caffeine-containing beverages for 12 hours prior to this visit so that the test results will not be influenced by the food they eat or by the normal digestion process.

Blood Chemistry: A blood draw will be collected for choline concentrations as well glucose, cholesterol, and other factors that may impact or be reflective of vascular function/health. A needle will be inserted in an arm vein to draw blood (approximately 2 tablespoons/draw).

Urine Test: Subjects will be asked to urinate in a small cup. Sodium and other electrolytes, glucose, protein, pH, and whether there are blood cells present will be measured to determine whether it is safe for each individual to participate in the study.

Proof of COVID-19 vaccination: Subjects will be asked to bring their vaccination card against COVID-19 to the laboratory.

Medical History: Subjects will be asked to complete a medical history questionnaire, which will be used to screen for health problems (unstable heart disease) or other reasons (medications which influence study results) that would preclude participation.

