## VT 18-535 Short Term Choline Supplementation and Cardiovascular Health in Adults

Endothelium Independent Vasodilation: This will be assessed by measuring brachial arterial dilation for 5 minutes following administration of 0.4 mg of sublingual nitroglycerine. Individuals will not be allowed to participate in this aspect if they take Cialis or Viagra or have a history of coronary heart disease.

24-hour Urine Collection: Subjects will be asked to collect all urine samples over a 24-hour period and bring the sample back to the laboratory during their next scheduled visit. All supplies and instructions will be provided by the laboratory.

Body Mass and Composition: Body weight will be measured on a digital scale accurate to +0.01 kg. Height will be measured with a stadiometer. Percent body fat and fat-free mass will be measured in all subjects using dual-energy x-ray absorptiometry (DEXA) (Prodigy Advance, GE Healthcare).

Pregnancy Test: If a subject is female and pre- or peri-menopausal or not postmenopausal for at least 1 year, she will be required to provide a small cup of urine for a pregnancy test.

Session 4, 10, 13, 19: (Approximately 3 hours) Garvin Building, Suite 1575

Overnight Fast: Subjects will be asked to avoid eating or drinking anything except water and to avoid consuming any caffeine-containing beverages for 12 hours prior to this visit so that the test results will not be influenced by the food they eat or by the normal digestion process.

Resting Blood Pressure and Heart Rate: Blood pressure measurements will be made under quiet, comfortable ambient laboratory conditions via mercury sphygmomanometry or an automatic blood pressure monitor. Heart rate will also be determined by an automatic blood pressure cuff. Measurements will conform strictly to American Heart Association guidelines.

Body Mass: Body weight will be measured on a digital scale accurate to +/- 0.01 kg.

Dietary intake analysis (24-hour recall): Subjects will be asked to recall all the food and beverages they consumed in the previous 24-hour period.

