Mixed Meal Tolerance Test: A small plastic tube (catheter) will be placed in one of the subject's arm veins. After a baseline blood draw to measure glucose, insulin, cholesterol, and other factors that may impact or be reflective of the subject's health status (e.g., C-reactive protein), the subject will drink a mixed meal beverage (Ensure original plus ®, 350 calories, 48g carbohydrate, 11g fat, and 16g protein) and blood will be collected in small amounts (less than one half teaspoon) at timepoints 0, 30, 60, 90, and 120 over a two-hour period.

Continuous Glucose Monitoring: The device which was placed on the subject will be removed.

Choline Supplement/Placebo: Subjects will be given enough capsules to last one week and asked to consume 1000 mg (2 x 500 mg tablets) of choline or placebo with a bottle of water every day.

Sessions 5-7, 14-16: (Approximately 30 minutes per session) Garvin Bldg, Suite 1575

Choline Supplement/Placebo: Subjects will be given enough capsules to last one week and asked to consume 1000 mg (2 x 500 mg tablets) of choline or the placebo with a bottle of water every day.

Resting Blood Pressure and Heart Rate: Blood pressure measurements will be made under quiet, comfortable ambient laboratory conditions via mercury sphygmomanometry or an automatic blood pressure monitor. Heart rate will also be determined by an automatic blood pressure cuff. Measurements will conform strictly to American Heart Association guidelines.

Body Mass: Body weight will be measured on a digital scale accurate to +/- 0.01 kg.

Dietary intake analysis (24-hour recall): Subjects will be asked to recall all the food and beverages they consumed in the previous 24-hour period.

After session 10: Following this session, subjects will return to their normal activities for a two-week "washout".

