**Continuous Glucose Monitor:** The placement procedure requires a sensor being inserted into the back side of the upper arm of the subject. When the wire-like sensor is deployed by the researcher, the subject can expect a sensation similar to a needle insertion for a blood draw. Potential risks associated here include discomfort during the insertion, pain, inflammation, redness, swelling, minor bleeding and minor infection at the site. These risks will be minimized by having a trained individual perform the procedure and this will be performed in aseptic conditions. Subjects might also experience these symptoms as a result of contact between the adhesive pad of the sensor and the skin. In rare cases, an infection can spread to other parts of the body. Allergic reactions can develop in response to the adhesive used to keep the CGM in place. If these symptoms occur, subjects

have the ability to remove the CGM at-will and can anticipate that their symptoms will clear up within a short time.

*17.2 Indicate the measures you will use to minimize risks and monitor subjects for safety. (e.g., asking a subject at regular intervals to rate how they are feeling from 1 to 10, or to slowly crouch in order to check their balance.)*

Blood Draw: The P.I. or a trained technician will perform all blood draws. Aseptic conditions will be followed during all of the procedures. Universal precautions will be taken in collection and handling of all blood samples. Subjects will be informed that their blood will be analyzed for presence of HIV and Hepatitis if an experimenter is exposed to their blood.

Endothelial Function: The risk of low blood pressure during nitroglycerine administration is minimized because the subject is already in the supine position. There is a small risk of a headache, but this will last only a few minutes. Individuals taking Cialis or Viagra cannot participate in this aspect of the study.

DEXA scan: The DEXA procedure will be performed by trained staff. Subjects will be informed of the risk of radiation exposure prior to study enrollment.

Whilst in the laboratory, each subject will be constantly monitored by the investigators and asked at regular intervals about how they are feeling. Furthermore, they will be made aware of their right to withdraw or discontinue any aspect of the protocol at any time.

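### Section 8.2 lists capsules at sessions 10 and 19, against the four-week schedule; once that is corrected, the specific side-effect question in 21.1 is not scheduled right after the last capsule week

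*Combined protocol and SAP*

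**What the plan says.** All references are to the combined protocol and SAP.

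- **Dosing (8.1).** Participants "consume either choline or a placebo (maltodextrin) supplement for four weeks" in each period, and there are "three-day testing sessions before and after the four-week period of choline and placebo supplement".
- **Supply (8.2).** At each hand-out, "Subjects will be given enough capsules to last one week". This line appears in the block for sessions 5–7 and 14–16. It also appears in the block headed "Session 4, 10, 13, 19: (Approximately 3 hours) Garvin Building, Suite 1575", so sessions 10 and 19 carry it as well as 4 and 13.
- **Washout (8.2, after session 10).** "Following this session, subjects will return to their normal activities for a two-week" washout.
- **Specific side-effect question (21.1).** "Subjects will be queried at the laboratory visits when supplements are provided as to any side effects or changes in health status". Reported side effects go to the investigator at once.
- **General check (17.2).** In the laboratory, participants are monitored and "asked at regular intervals about how they are feeling".
- **Review table (21.1).** The side-effects row covers test meals and procedures but not the supplement. It is timed to a daily meal pick-up, which no visit in section 8 contains.

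**The concern.** Two rules in the plan do not fit together. If 8.2 is followed as listed, staff give out a fifth week of capsules as the washout begins, and another at the final visit. If 8.1 is followed, sessions 10 and 19 are not supply visits, and the trigger for the 21.1 question is gone from the whole post-treatment block. Removing the surplus hand-outs without touching 21.1 would therefore remove the specific question that would have followed the last dosing week.

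At stake is how fully and how well dated the supplement complaints are. The first safety endpoint in 4.2 concerns gastrointestinal complaints with the capsules, and 14.1 names acceptability among the purposes of the pilot. Immediate referral to the investigator and the semi-annual review of adverse event rates both work only on what has been reported. A complaint from week 4 that has already settled would have to come up in the general check, be volunteered, or, in period 1 only, be recalled after the washout.

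**Working it through.** **Inputs.** One week of capsules per hand-out, and a two-week washout after session 10 (8.2). Four weeks of dosing per period, with a test block before and after (8.1). Visit times (1.0). About 12 weeks, 19 visits and 36 hours (11.1). Glucose sensor placed at the first and removed at the third session of a block, worn 3–4 days (8.2). 60 participants (14.1).

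**1. Reproduce the plan's own figures.** Visits: 1 + 4 + 4 + 4 + 6 = 19. Hours, with the times in 1.0: 1 + 4×3 + 4×2 + 4×3 + 6×0.5 = 36. Both match.

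**2. Count the weeks supplied per period.**
- Hand-outs at sessions 4–7 and 13–16: 4 × 1 = 4 weeks, as in 8.1.
- Hand-outs also at 10 and 19, as 8.2 lists: 5 × 1 = 5 weeks, which does not match.

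The surplus is 2 weekly supplies per person, or 2 × 60 = 120 over the study. If the supply from session 10 were taken, it would use 7 of the 14 washout days.

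**3. Find the next 21.1 question after the last capsule week.**

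| Schedule | Week handed out at session 7 | Week handed out at session 16 |
|---|---|---|
| Four weeks (8.1) | session 13 | none |
| 8.2 as listed | session 10 | session 19 |

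**4. Delay in period 1 on the four-week schedule.** Assume that weekly visits are kept and that each test block spans *s* = 2 to 4 days from first to third session. Session 13 follows session 8 by one block, the washout and a second block: 14 + 2*s*, which is 18 days for *s* = 2 and 22 for *s* = 4. If the last capsule is taken the day before session 8, add one day: 19–23. The range is about 18–23 days.

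**5. Timeline check.** Sessions 2 to 19 take 28 + 14 + 28 + 4*s* days: 78 days (11.1 weeks) for *s* = 2 and 86 days (12.3 weeks) for *s* = 4. This agrees with the 12 weeks of 11.1. It does not decide between the two schedules, because a fifth week given at session 10 would fall inside the washout. The conflict with 8.1 and with the washout decides it.

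**6. What still happens in the post-treatment blocks.** Scheduled contact is 3 + 2 + 3 = 8 hours at sessions 8–10 and again at 17–19, with the 17.2 check throughout. Out-of-range blood pressure and laboratory values are also discussed under 21.1, but that is not a side-effect question.

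**7. After the fix.** A question at sessions 8 and 17 follows the last capsule week by about a day at most in both periods.

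**The case against.** The strongest reply is that the participant is seen for 8 hours straight after week 4 and is asked repeatedly how they feel. A reader might infer from the schedule that week 4 goes unmonitored, or that a fixed share of dosing days is uncovered. The documents do not support that. Section 21.1 states no look-back period any more than 17.2 does. It also does not say that side effects are taken only at supply visits, and any reported side effect is referred whenever it arises. This part of the reply stands: the difference is between a specific and a general question.

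Second, 8.2 read literally triggers the question at sessions 10 and 19, and the gap closes. That is true, but only by dispensing a fifth week against 8.1 and into the washout. The text needs correcting on either reading.

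Third, the consequence is small. Severe distress is unlikely to go unmentioned over three staffed visits. Section 7.2 links the listed side effects to intakes above 3500 mg/day, while the dose is 1000 mg/day. This also stands, and it limits the severity.

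A reader might also suspect a bias between the products. The missing question falls at the same place in each period whichever product is taken, and each product comes second in one sequence. Section 5.2 names no safety comparison. No such bias follows, given roughly balanced sequences.

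**Conclusion.** The concern holds as a minor inconsistency. The capsule supply listed at sessions 10 and 19 contradicts the four-week period and the washout. With that corrected, the specific 21.1 question is not scheduled in either post-treatment block. In period 1 it next comes about 18–23 days after the last capsule, and in period 2 it does not come again. The delay rests on assumed block spans of 2–4 days and on weekly visits being kept; the absence in period 2 does not depend on them.

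This is a loss of specific, dated questioning about the capsules at the end of each period. It is not a count of missed events: the documents give no event rate, and nothing in them points to problems confined to week 4. Efficacy estimates and sample size are not touched by the questioning gap.

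**What to change.** 1. **8.2:** delete the capsule supply from sessions 10 and 19, leaving it at 4 and 13 (and at 5–7 and 14–16).
2. **21.1 text:** keep the question at supply visits and add it at the first post-treatment visit of each period, sessions 8 and 17. Have it cover the time since the last visit and record the onset date. Asking at 9–10 and 18–19 as well is optional.
3. **21.1 table:** add the supplement to the side-effects row, keep test meals and procedures, and replace the meal pick-up timing with one that matches the visit schedule.

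Items 1 and 2 should be made together, since item 1 alone removes the trigger at sessions 10 and 19.

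**Cost.** Two extra questions per person, 2 × 60 = 120 in total, at visits already attended. At an assumed 1–5 minutes each, that is 2–10 minutes per person against about 36 hours. Asking at all six post-treatment visits would make 6 × 60 = 360. The downside is that one complaint may be recorded twice; the onset date lets duplicates be merged. No visit or test is added, and blinding is unchanged.
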